
[figure not shown]
1. Non-medical use of psychoactive drugs other than, nicotine, alcohol, or caffeine 3 month prior to the Screening Visit;
2. History of or current evidence of significant medical (e.g. seizure disorder) or psychiatric illness (e.g. psychosis) judged by the investigator to put the participant at greater risk of experiencing an adverse event due to exposure or completion of other study procedures.
3. Use of an OTC, systemic or topical drug(s), herbal supplement(s), or vitamin(s) within 14 days or 5 half-lives of active drug (whichever is longest) prior to experimental sessions; which, in the opinion of the investigator or sponsor, will interfere with the study result or the safety of the subject.
4. Use of a prescription medication (with the exception of birth control prescriptions) within 14 days of experimental sessions; which, in the opinion of the investigator or sponsor, will interfere with the study result or the safety of the subject.
5. Use of dronabinol (Marinol®) within the past month.
6. Average use of cannabis more than 2 times per week in the prior 3 months.
7. History of clinically significant cardiac arrhythmias or vasospastic disease (e.g., Prinzmetal's angina).
8. Enrolled in another clinical trial or have received any drug as part of a research study within 30 days prior to dosing.
9. Having previously sought medical attention to manage adverse effects following acute cannabis use.
10. Individuals with anemia or who have donated blood in the prior 30 days

6. Drugs/ Substances/ Devices

- a. The rationale for choosing the drug and dose or for choosing the device to be used.

The THC for this study will be of GMP quality and manufactured and distributed to JHU by THC Pharm GmbH (Frankfurt, Germany) in accordance with federal regulations. THC Pharm GmbH will supply pure THC in a resinous form. The THC will be suspended in pharmacy-grade ethanol (190 proof) to create a solution that is approximately 10% THC/ 90% ethanol (this will increase the ease and precision of dosing measurements for THC, given the small doses that will be used). The ethanol solution will be purchased from Spectrum Chemical (product code: ET108; see appendix materials for product specifications), and meets standards for use in drug preparations intended for humans. Prior to pulmonary administration, the ethanol will be dissipated from the heating pad used for THC administration. The Mighty Medic is an approved medical device for administration of THC in Germany and Canada and can reliably deliver cannabinoids with similar effectiveness to the Volcano Medic device (made by the same manufacturer), which has been used to deliver THC in research studies elsewhere (including in our laboratory).

The d-limonene for this study is >99% purity, meets GMP specifications, and will be obtained from True Terpenes. Analytical testing conducted by [name], at RTI International indicates that the Volcano Medic reliably delivers d-limonene in a linear dose-response manner, and that recovery of d-limonene from the Volcano Medic balloons via GC/MS has little variability and does not differ whether the terpene is injected directly into the balloon and equilibrated with laboratory air or vaporized at 210°C using the Volcano Medic as will be done in the current study (see below Figure for triplicate testing via both methods). Given that the Mighty Medic and Volcano Medic are demonstrated to deliver comparable levels of cannabinoids and given that we will use the same temperature settings (210°C) for the Mighty Medic to vaporize THC and limonene, these analytical test results for the Volcano Medic are generalizable to the Mighty Medic.

The selection of doses was conducted to balance the study aim, participant safety and tolerability based on previous experience, and ensuring that doses are ecologically valid. In our laboratory, tolerant daily cannabis users have safely self-administered up to 3 grams of smoked cannabis containing 10% THC (300mg THC) within one hour (protocol NA_00082269). More recently, acute oral, smoked and vaporized administration of 10mg and 25mg THC to infrequent cannabis users (as will be recruited here) resulted in dose-dependent drug effects (IRB00035394). At the 10mg dose, participants reported an increase in pleasant drug effects with few unpleasant side effects. At the 25mg dose, there was no change in ratings of pleasant drug effects, but unpleasant drug effects, including self-reported ratings of anxiety, were significantly increased. Because the aim of the present study is to evaluate whether d-limonene can attenuate THC-induced anxiety, the selected THC doses represent what are likely to a good range from which to evaluate these effects. The low THC dose (15 mg) is intermediate to the 10 mg (no anxiety) and 25 mg (mild to moderate anxiety) doses we used in our recent protocol and is expected to serve as a positive control dose, although low levels of anxiety may be observed. The 30 mg dose is expected to produce anxiety in most study participants, but not severe anxiety in the target study population.

If initial testing in this study indicates difficulty with dose tolerability, or a lack of anxiety at either dose, then we will revise the proposed doses accordingly. Adverse events beyond anxiety, sedation, or nausea (vomiting in rare instances) are unlikely given the relatively safe pharmacological profile of THC (partial agonist), which has no history of being directly associated with fatalities. In cases where a participant experiences panic and or paranoid reactions, research staff will engage the person in relaxation exercises and will suspend research procedures until the volunteer has regained comfort. These types of effects are typically of short duration and our staff is well practiced in helping manage these types of effects. In the case of an extreme adverse reaction, we will call 911 and participants will be taken to the Johns Hopkins Bayview ER for treatment.

The d-limonene doses employed in this study (1, 5, 15 mg) were derived based on previous experiments outlined in the background (cf. Falk et al., 1990; Falk-Filipsson et al., 1993) and the known ratios of terpenes and THC in cannabis currently being used in legal markets in the U.S. and Canada. We are not aware of any serious adverse events occurring after inhalation of d-limonene. It is commonly inhaled in ambient air due to exposure to citrus fruits, household cleaners or air fresheners, candles, or a variety of other products containing citrus essential oils.

The Mighty Medic is an approved medical device in the European Union, Canada and Israel for inhalation of THC or cannabis (see certificate in Annex documents). The rationale behind its use is to volatilize cannabinoids and cannabis terpenoids at a temperature below that which combusts the material, and produces polyaromatic hydrocarbons (Abrams et al. 2007, Hazekamp et al. 2006, Zuurman et al. 2008).

- b. Justification and safety information if FDA approved drugs will be administered for non-FDA approved indications or if doses or routes of administration or participant populations are changed.

THC is FDA approved as an oral formulation (dronabinol; Marinol). D-limonene is Generally Recognized as Safe (GRAS) for oral consumption. As detailed above, we believe that the THC and d-limonene administration in this study will be safe for cannabis-experienced participants. The route of administration (vaporization) is common for cannabis self-administration and the doses of both THC and d-limonene are within the range of what would be expected in real-world cannabis use scenarios. We have submitted and IND application to the FDA for the conduct of this experiment.

- c. Justification and safety information if non-FDA approved drugs without an IND will be administered.

N/A

Study Statistics

- a. Primary outcome variable.

The primary outcome variable for this study is self-reported rating of "Anxiety" on the DEQ.

- b. Secondary outcome variables.

Secondary outcome variables include self-reported drug effect and mood ratings on additional items of the DEQ and STAI, vital signs, cognitive performance, and Cmax of THC and 11-OH-THC in plasma.

The sample size estimate for this study was based on previous work in this laboratory evaluating dose effects of acute drug administration using a within-subjects design. A meta-analysis was previously conducted comparing the statistical power of 13 drug effect assessments from six dose-effect studies, with 14 participants each, evaluating a range of abused drugs in our laboratory (Felch, Di Marino, and Griffiths 1996). The analysis showed that average effect size for primary measures (i.e. subjective drug effect ratings, staff ratings and behavioral/cognitive performance measures) ranged from approximately 0.87 to 1.0. Based on this estimate of effect size, the proposed sample size of 20 should be adequate to assess the expected effects and to differentiate low from high doses. This sample selection methodology has been consistent in our long history of studies investigating dose-effects comparisons of different drugs, which have demonstrated excellent external validity and have become the FDA recommended standard for human abuse liability assessment. Subjective drug effect and mood ratings, vital signs and cognitive performance outcomes will be assessed using multiple regression analyses appropriate for repeated measures testing based on the final characteristics of the data set (e.g. normal distribution, skewness, kurtosis).

- c. Early stopping rules.

The study will be stopped if new information is learned that indicates a serious risk to study participants.

7. Risks

- a. Medical risks, listing all procedures, their major and minor risks and expected frequency.

Potential risks of THC exposure include dizziness, change in blood pressure, red or irritated eyes, drowsiness, easy laughing, euphoria, rapid heart rate, orthostatic hypotension, dry mouth, jitters, headache, nausea, vomiting, increased appetite, perceptual difficulties, memory lapse, hallucinations, confusion, depression, paranoid reaction, depersonalization, and rash. An additional potential risk of THC and/or terpenoid inhalation is coughing. Available preclinical and clinical evidence indicates that d-limonene does not pose a mutagenic, carcinogenic, genotoxic, nephrotoxic, or teratogenic risk to humans. In a prior experiment involving pulmonary inhalation of d-limonene at air concentrations that approximate the level of exposure expected in the present study (Falk-Filipsson et al., 1993), d-limonene exposure was not associated with any discomfort in the eyes, nose, or throat, and no CNS-related symptoms (e.g., "headache," "fatigue," "sick," "dizziness," "difficulty breathing") were different from placebo. Exposure to d-limonene with THC may modulate or accentuate certain effects, and there is always the possibility of paradoxical reactions. However, we feel that the risk of serious adverse events related to THC or d-limonene exposure in this study is minimal, inasmuch as participants are experienced cannabis users and the doses we are administering are within the range by which most participants are likely to have encountered these substances through naturalistic cannabis use.

Venous blood sampling may cause pain, tenderness, bruising, or bleeding at the needle puncture site. Some subjects may feel transient lightheadedness or dizziness, or lose consciousness (syncope), because of anxiety and vasovagal reaction.

A further risk is that participants may mistake the proposed studies as treatment or may delay treatment seeking in order to participate, although this is unlikely since we are targeting occasional users.

Breach of confidentiality about self-reported drug use and biological tests indicating recent drug use is also a risk.

Exposure to COVID-19 is a risk.

b. Steps taken to minimize the risks.

Participants are not a "vulnerable population" as defined by human subject protection guidelines; that is, they are not minors, pregnant women, under legal coercion or restriction, or mentally impaired. They are competent adults who provide their voluntary informed consent. Participants will be recruited via media advertisements and posters that clearly state the nature and intent of the study. The consent process will inform the participant in detail of the procedures, time involvement, compensation, risk, and treatment options other than participation in our study. Particular emphasis will be given to providing information regarding the potential risks involved with taking the study drugs. Volunteers will also be instructed that they may withdraw from participation at any time without losing any of the compensation that they have earned to that point.

It is unlikely that any adverse event should arise that requires immediate medical or psychiatric treatment. However, in case of an adverse event, participants will be under the supervision of medical/nursing staff throughout the study. The medical and nursing staff at BPRU are trained in CPR and mobile emergency crash carts are available on the same corridor where all experimental procedures will be conducted. The research facility (BPRU) is located directly across the street from the Johns Hopkins Bayview Medical Center Emergency Department, and, in case of an adverse event, staff will call 911 and participants will be taken by EMTs for immediate care. The Principal Investigator will be immediately notified of any serious adverse events that arise.

If participants develop nausea or vomiting after vaporization, study staff will assist the affected participant(s) appropriately and contact the study PI and BPRU medical staff. Nursing staff will be on site during all experimental test sessions and a physician is always on call.

Blood collection risk will be minimized by performing venipuncture while participants are sitting down, and by having them remain under staff observation until it is clear that no acute adverse effects occur as a

result of the procedure. The risk of infection is negligible because standard sterile technique will be used. Venipuncture poses a risk of infection or thrombophlebitis, which increases with duration of placement. This risk is minimized by use of careful sterile technique, having nursing staff check the venipuncture site (with prompt attention if there are clinically significant signs or symptoms such as tenderness, swelling, or redness). The risk of anemia is negligible because the total amount of blood to be collected (up to 360 mL) during the entire completed study is less than the amount (473 mL) collected within one hour during a single blood donation session. The amount of blood loss will be readily replaced without harm to study participants.

All advertisements and the informed consent process will clearly indicate that this research is designated only for those not seeking treatment, that participation is not a substitute for treatment, and that participation offers no clinical benefit. They will be clearly informed that they will be asked to inhale cannabis components during their participation. Any participant who expresses an interest in receiving immediate treatment for cannabis or other substance use will be referred to a community treatment clinic. If this occurs during the study, their participation in the study will be terminated. As previously described, participants will be instructed that should they withdraw from the study at any point to pursue treatment they will still be compensated for their participation up until that point in the study.

Until risk of exposure to COVID-19 is no longer a public health concern, we will maintain social distancing throughout the study procedures to the extent possible. All staff and study participants will be required to wear PPE appropriate to the nature of the tasks being completed and distance to others (e.g. face masks when maintaining social distancing, face masks, face shields, and disposable gloves when closer than 6ft). We will also minimize the number of staff who come in contact with any single participant to the extent possible based on duties to be performed and staff availability. Our target will be to have each participant only interact with 3 staff (medical staff member for physical evaluation, nurse for blood draws, research staff member for all other procedures).

c. Plan for reporting unanticipated problems or study deviations.

Study personnel will also follow ICH regulations (detailed in *Clinical Safety Data Management, Definitions, and Standards for Expedited Reporting*) regarding reporting of adverse events and all study deviations to the IRB and study sponsor.

d. Legal risks such as the risks that would be associated with breach of confidentiality.

Participants' names will be recorded only on the screening, informed consent, and necessary medical and payment forms. Anonymous participant identification numbers will be used on all other forms and labeling of biological fluids and test results. All information gathered will be kept in locked research staff offices or file cabinets. All medical information obtained will be handled in accordance with HIPAA regulations. Only research staff will have access to participant records. The limits of confidentiality (e.g. suspected child abuse or neglect, or harm to self or others) will be discussed in detail with the participants during the informed consent process. To reduce the likelihood of patient records disclosure we have obtained a Certificate of Confidentiality.

e. Financial risks to the participants.

This study does not involve patients receiving treatment; therefore, the financial risks are minimal. Participants will be fairly compensated for their time and effort in complying with the study protocol.

8. Benefits

a. Description of the probable benefits for the participant and for society.

The primary benefit of the proposed research is in the knowledge gained regarding the pulmonary inhalation of THC and d-limonene alone and in combination. This knowledge will advance our basic scientific understanding of both substances and may guide policy and regulations related to cannabis. The study will also extend the extant literature investigating the acute dose effects of

inhaled THC, including subjective effects, cognitive performance, and their correlation with biological cannabinoid levels. These experiments may objectively demonstrate synergy of cannabis components and the modulating and even beneficial effects of cannabis terpenoids on THC. The results could benefit the research community in finding and developing selected cannabis chemovars with unusual cannabinoid and terpenoid contents and ratios for improved efficacy and optimized therapeutic index. Because we anticipate relatively minor risks to these cannabis experienced study participants, we feel that the proposed research has a positive risk-benefit ratio.

9. Payment and Remuneration

a. Detail compensation for participants including possible total compensation, proposed bonus, and any proposed reductions or penalties for not completing the protocol.

All participants will be compensated \$30 for completing the screening assessment, up to \$2700 for completing each of 9 outpatient sessions, and \$500 in completion bonuses resulting in \$3230 of total possible earnings for completing the entire study. Those who complete the optional 10th study session will be paid an additional \$300, thus earning a total of \$3530. Compensation of this magnitude is appropriate given the length and nature of this study. Calculations are as follows:

Screening Visit:	\$30
Outpatient Sessions 1-9:	\$300/day (\$2700 total)
Completion Bonus:	\$500
Optional 10 th study session:	\$300
Total Compensation for 9 main visits:	\$3230
Total Compensation for 9 main visits +optional 10 th visit:	\$3530

Study participants will receive an additional \$300 for any test session that is repeated due to data loss. There will not be any change to the study completion bonus for repeat testing.

10. Costs

a. Detail costs of study procedure(s) or drug (s) or substance(s) to participants and identify who will pay for them.

The only direct costs to the participants will be their transportation to and from Bayview for each study visit. That cost has been factored into the compensation for participating.

Reference List

Abrams, D. I., H. P. Vizoso, S. B. Shade, C. Jay, M. E. Kelly, and N. L. Benowitz. 2007. "Vaporization as a smokeless cannabis delivery system: a pilot study." *Clin Pharmacol Ther* 82 (5):572-8.

Bloor, R. N., T. S. Wang, P. Spanel, and D. Smith. 2008. "Ammonia release from heated 'street' cannabis leaf and its potential toxic effects on cannabis users." *Addiction* 103 (10):1671-7. doi: 10.1111/j.1360-0443.2008.02281.x.

Bowles, E. J. 2003. *The chemistry of aromatherapeutic oils*. 3rd ed. Crow's Nest, NSW, Australia: Allen & Unwin.

Buchbauer, G. 2010. "Biological activities of essential oils." In *Handbook of essential oils: science, technology, and applications*., edited by K. H. C. Baser and G. Buchbauer, 235-280. Boca Raton, FL: CRC Press.

Buchbauer, G., L. Jirovetz, W. Jager, C. Plank, and H. Dietrich. 1993. "Fragrance compounds and essential oils with sedative effects upon inhalation." *J Pharm Sci* 82 (6):660-4.

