Protocol Overview. The proposed study will be conducted at the Johns Hopkins Behavioral Pharmacology Research Unit (BPRU). The purpose of the study is to examine the behavioral pharmacology of THC, d-limonene, and their combination versus placebo. All procedures will be performed in double-blind manner using a within-subject crossover design. Participants will be healthy adults with a history of having experienced mild to moderate anxiety following acute cannabis exposure, but will not be daily cannabis users. A total of 9 primary outpatient drug administration sessions will be conducted for each evaluable participant. Study completers who report increased anxiety after THC exposure will be invited to complete an optional 10th study condition with a higher dose of d-limonene.

- 1) Placebo (5mL distilled water)
- 2) THC (15 mg)
- 3) THC (30 mg)
- 4) D-Limonene (1 mg)

- 5) D-Limonene (5 mg)
- 6) THC (15 mg) + D-Limonene (1 mg)
- 7) THC (30 mg) + D-Limonene (1 mg)
- 8) THC (15 mg) + D-Limonene (5 mg)
- 9) THC (30 mg) + D-Limonene (5 mg)
- 10) THC (30 mg) + D-Limonene (15 mg) – optional for select study completers only

We will obtain a battery of pharmacodynamic outcome measures at baseline and for 6 hours after each dose. Sessions will be conducted at a target rate of 1-2 times per week, with a minimum of 3 days between experimental sessions. We will recruit study volunteers until 20 participants complete the protocol. Participants who drop out of the study prior to completion of all scheduled sessions will be considered “incomplete” and will be replaced. Drug administration sessions will be completed in a randomized order because there are too many dose conditions to properly counterbalance the order across 20 study completers. The optional 10th condition will not be randomized and will only occur after the other nine study conditions have been completed and the PI has determined that the participant exhibited an anxiogenic response to THC during initial test sessions.

Participants. We will recruit and consent up to 65 research volunteers in order to obtain 20 study completers. We anticipate that about 50% of those screened will not be eligible or interested in the study, and that post-randomization some participants may drop out of the study before completion. It is estimated that we will need to randomize 32 participants to achieve 20 completers given the length of the protocol.

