Study drugs, pure THC in ethanol, pure d-limonene, or placebo (distilled water), will be delivered via vaporization using the Mighty Medic (Storz-Bickel, Tuttlingen, Germany), a commercial vaporizer designed specifically for the delivery of cannabis and THC. Vaporization was selected as the route of administration because THC and limonene have good pulmonary bioavailability, it allows for more precise dose delivery versus smoked or oral routes, this method is most likely to protect the blind of drug conditions between sessions as there are fewer sensory cues associated with inhalation of vapor versus smoked cannabis, inhalation is the most common method of consuming cannabis, and because vaporization has the same pharmacokinetics, but less pulmonary risk compared with smoking. The Mighty Medic employs hot air at a temperature of 210°C to vaporize THC and terpenoids without combustion, thereby limiting exposure to potentially carcinogenic polycyclic aromatic hydrocarbons, ammonia, and other toxins. Each drug dose is placed in a small dosing capsule (or “pod”). Participants inhale the contents of the capsule by inhaling through a mouthpiece attached to the vaporizer. This activates the heating element and delivers the study drug. A new mouthpiece tip will be used for each experimental session, and a new vaporizer will be used for each study participant. The Mighty Medic is an approved medical device in the European Union, Canada and Israel and functions similarly to the Volcano Medic, which we have used previously in our laboratory to administer raw cannabis via vaporization. The Mighty Medic and Volcano Medic are made by the same company: Storz-Bickel. Analytical testing conducted by Research Triangle Institute and others has demonstrated that the Volcano Medic reliably and dose-dependently delivers THC and d-limonene. Importantly, analytical testing conducted by Storz and Bickel has revealed that the Volcano Medic and Mighty Medic are equally effective at delivering THC in vapor. Currently, there are no regulatory limits in the U.S. on the allowable concentration of d-limonene in ambient air, and the total exposure during an acute dose session in this study is likely not more than what one would be exposed to peeling an orange or walking down an aisle of cleaning supplies at a grocery store.

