A pharmacist or other qualified technician will apply test substances with a micro-pipette into a dosing capsule, accessories that come with the Mighty Medic. For each experimental session, a dosing capsule with the assigned dose will be provided for participant self-administration using the Mighty Medic in accordance with the manufacturers operating instructions. When the Mighty Medic is activated, the dosing capsule is heated, vaporizing the substances placed inside it.

At each session, study personnel will first purge residual ethanol in the Mighty Medic in an unheated state. Detailed instructions for use of the device are available here: <https://www.storz-bickel.com/media/wysiwyg/CRAFTY-MIGHTY/PDF/mighty-vaporizer-instructions-manual.pdf> (see annex documents) and are provided in the supplementary materials section of the IRB application.

Participants will then inhale the contents of one Mighty Medic dosing capsule. Specifically, they will be given 15 minutes to inhale the contents of the capsule *ad libitum* (i.e., at their own pace). Participants will take a minimum of 15 puffs. If a visible vapor is still observed after 15 puffs, the will continue to take puffs until they no longer exhale visible vapor (this signifies that the dosing capsule is depleted; see detailed instructional materials from Storz and Bickel). This procedure will produce THC exposure of 0, or 15mg or 30mg THC, and 1mg, 5mg, or 15mg d-limonene. Participants will be able to halt self-administration of the study drug if they experience adverse effects prior to inhaling the entire dose. Similarly, study staff may halt the drug administration procedure if untoward drug effects are observed. This is not expected at the doses under investigation, but may occur in rare circumstances. Study participants and research staff will be blinded to dose assignment. The conclusion of drug administration will be considered the “0 hour” by which remaining protocol assessments will be scheduled. To prevent issues of cross-contamination, new inhalation bags and thoroughly cleaned stainless steel wool pads will be utilized for every test session.

Post-Drug Administration Procedures.

Following the “0-hour” time point (last exhalation of study drug), participants will complete a battery of assessments that includes:

- 1) Serum specimen collection at 0min, 15 min, 60 min, 120 min, and 180 min.

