A placebo dosing session (no THC, no terpenoid) will be included to help interpret active drug effects on pharmacodynamic outcomes. Placebo dosing provides a control for expectancy effects on subjective reports and cognitive performance as well as non-pharmacological factors such as fatigue, hunger, and learning effects on performance tasks. Placebo dosing is standard for research studies involving evaluation of acute drug effects.

g. Definition of treatment failure or participant removal criteria.

This is not a treatment study. Participants may quit participation at any time of their own volition. The study investigators will discharge study participants for failing to attend their scheduled session, failure to follow the protocol requirements, or for other reasons not known at this time.

h. Description of what happens to participants receiving therapy when study ends or if a participant's participation in the study ends prematurely.

This is not a treatment trial; there is no direct course of therapy related to the participant population being targeted. We are recruiting healthy adults with experience using cannabis and who are not seeking treatment for substance use problems. Should any report the desire for treatment they will be referred to appropriate community service centers. Premature termination of participation may result in the need to recruit additional research volunteers, but should have no impact on the study volunteer directly.

5. Inclusion/Exclusion Criteria

Participants will meet the following eligibility criteria:

Inclusion Criteria

1. Have provided written informed consent
2. Be between the ages of 18 and 55
3. Be in good general health based on a physical examination, medical history, vital signs, 12-lead ECG and screening urine and blood tests
4. Test negative for drugs of abuse other than cannabis, including breath alcohol at the screening visit and at clinic admission
5. Not be pregnant or nursing (if female). All females must have a negative serum pregnancy test at the screening visit and a negative urine pregnancy test at clinic admission.
6. Have a body mass index (BMI) in the range of 18 to 36 kg/m²
7. Blood pressure at Screening Visit does not exceed a systolic blood pressure (SBP) of 150 mmHg or a diastolic blood pressure (DBP) of 90 mmHg
8. Have no allergies to any of the ingredients used to prepare vapor (THC, d-limonene).
9. Report having experienced anxiety after consuming cannabis in the past.

Exclusion Criteria

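### The placebo is specified as 5 mL of water, at least 13 times the liquid implied for any primary active dose, which conflicts with the capsule-loading procedure and could make placebo sessions recognisable

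*Protocol*

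**What the plan says.** The Protocol Overview in section 4 lists the placebo condition as "Placebo (5mL distilled water". Under Experimental Drug Exposure in the same section, the three materials are "pure THC in ethanol, pure d-limonene, or placebo (distilled water"), and each dose goes into a small capsule. A pharmacist or technician "will apply test substances with a micro-pipette into a dosing capsule", and one capsule is inhaled per session. Section 6a describes the THC stock as "a solution that is approximately 10% THC/ 90% ethanol" and the limonene as more than 99% pure, with no diluent mentioned.

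Two statements bear on the vehicle. Experimental Drug Exposure has staff purge residual ethanol, unheated, at each session. Section 6a has the ethanol driven off before inhalation.

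Inhalation lasts at least 15 puffs and then continues until no vapour is seen on exhalation. Participants and research staff are to be blinded. Section 4f gives the placebo its role: "Placebo dosing provides a control for expectancy effects on subjective reports and cognitive performance". The primary outcome (Study Statistics, item a) is a self-rating of anxiety.

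**The concern.** A placebo should differ from the active preparations only in its active content. Here the fill volume stated for placebo is of a different order from anything the rest of the protocol implies for the active conditions. No passage tops active capsules up with water, equalises volumes, or gives placebo and limonene-alone capsules the same liquid as the THC capsules.

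This matters because the end of inhalation is tied to visible vapour. A much larger or different liquid load could change how long vapour is seen or how many puffs are taken, in front of both participant and staff. Each completer goes through all nine primary conditions and can compare them. If placebo can be recognised, it no longer controls expectancy on self-rated outcomes. The exposed comparisons are those against placebo, above all limonene alone versus placebo, where no THC effect is present and the volume gap is widest.

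**Working it through.** The protocol gives no derivation of the 5 mL and no fill volume for any active condition, so there is no figure to reproduce. The active volumes have to be worked out from dose and concentration.

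**Inputs from the protocol**
- Placebo: 5 mL (section 4, Protocol Overview).
- THC doses: 15 and 30 mg. Limonene doses: 1, 5 and, optionally, 15 mg. From Experimental Drug Exposure: "This procedure will produce THC exposure of 0, or 15mg or 30mg THC, and 1mg, 5mg, or 15mg d-limonene".
- THC stock: about 10% THC (section 6a). Weight/volume or weight/weight is not stated.
- Limonene: more than 99% pure, treated as neat.

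**Assumption not in the protocol:** density 0.8-1.0 g/mL for both the THC solution and limonene. The upper end gives the same THC volumes as a 10% weight/volume reading (100 mg/mL).

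**THC solution:** volume = dose / 0.10 / density.
- 15 mg: 150 mg of solution, so 0.15 mL (density 1.0) to 0.1875 mL (density 0.8).
- 30 mg: 300 mg of solution, so 0.30 mL to 0.375 mL.

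**Neat limonene:** volume = dose / density.
- 1 mg: 1.0 to 1.25 microlitres.
- 5 mg: 5.0 to 6.25 microlitres.
- Optional 15 mg: 15 to 18.75 microlitres.

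**Largest totals**
- Primary conditions (30 mg THC + 5 mg limonene): 0.375 + 0.00625 = about 0.38 mL.
- Optional tenth condition (30 mg + 15 mg): 0.375 + 0.01875 = about 0.39 mL.

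**Placebo volume relative to active volume**

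| Active material | Volume | 5 mL divided by volume |
|---|---|---|
| 30 mg THC | 0.30-0.375 mL | 13.3-16.7 |
| 15 mg THC | 0.15-0.1875 mL | 26.7-33.3 |
| 5 mg limonene | 5.0-6.25 microlitres | 800-1000 |
| 1 mg limonene | 1.0-1.25 microlitres | 4000-5000 |

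**Could active capsules also hold 5 mL?** Not with the THC stock alone: at 100 mg/mL, 5 mL would contain 5 x 100 = 500 mg of THC. They would need a diluent that the protocol does not mention.

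**Vehicle:** ethanol is loaded in the six THC-containing primary conditions. It is not described for the other three of nine: placebo and the two limonene-alone conditions.

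**Which contrasts are touched?** THC alone versus THC plus limonene uses the same THC solution on both sides and differs by about 1-6 microlitres in the primary conditions. The water placebo does not enter that comparison.

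**The case against.** The strongest reply is that 5 mL is a wording error and was never delivered. If so, the ratios describe a mistake on paper and not a difference anyone inhaled. That is possible, and the protocol cannot settle it. The figure still stands in the operative list of conditions and disagrees with the loading procedure, so it needs correcting either way.

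The second reply is that the ethanol cue is largely dealt with, because residual ethanol is purged at each session and driven off before inhalation. This stands as far as ethanol goes. A reader might infer that the absence of ethanol identifies placebo and limonene-alone sessions; the purge makes that inference weak. The purge is not described as removing water or equalising volume.

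Third, the 15-puff minimum applies in every session and limits differences in puff count. That also stands in part, but puffing beyond 15 depends on visible vapour.

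Fourth, a reader might infer that the main question, whether limonene reduces THC-induced anxiety, is compromised. The documents do not support this, because that comparison does not use the water placebo and its two sides are nearly equal in volume.

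Fifth, it is tempting to say that 5 mL cannot fit the capsule. The capsule is called small, but its capacity is not given, so this is unproven.

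Finally, loading ethanol in every condition looks like the natural remedy. It is not shown to help: once purged, an ethanol-only placebo capsule would hold essentially nothing and might match the visible vapour less well than water.

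**Conclusion.** The point holds as an internal conflict with a plausible, unquantified consequence for blinding. The stated placebo volume is about 13-33 times the implied THC solution volumes and 800-5000 times the limonene-alone volumes. No primary active condition exceeds about 0.4 mL. This rests on a 10% stock, undiluted limonene and densities of 0.8-1.0 g/mL; the gap is too large for those assumptions to alter the conclusion.

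Weakened blinding is an inference from the volume mismatch and the visible-vapour rule. The protocol neither reports it nor allows its size to be computed. It concerns contrasts against placebo, chiefly limonene alone versus placebo, and leaves THC versus THC plus limonene largely untouched. The protocol should be corrected, but the defect does not undermine the trial's central comparison.

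**What to change.** Reconcile the Protocol Overview, Experimental Drug Exposure and section 6a, and correct the placebo volume. State one common total fill volume and the same purge step for all conditions, including placebo and limonene alone, so that volume does not identify the session. Do not require ethanol in every condition unless a check shows that it matches the visible vapour. Limonene's odour will remain a cue that volume matching cannot remove.

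The Background reports that 16 participants had been randomised when the 15 mg limonene amendment was submitted, against an expected 32 overall. The sponsor should therefore document what was actually loaded in placebo and limonene-alone sessions, record the date of any change in preparation, and interpret contrasts against placebo accordingly.

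If 5 mL is only a slip, the cost is a wording correction, a pharmacy worksheet entry and a short record of past practice. If preparation really changes, there is a further cost: two preparations would be mixed across, and possibly within, participants in a crossover, and the amendment would have to account for that. An IND application has been submitted (section 6b), so its consistency with the corrected text should be checked too.
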